9.5.4.2 Reporting of Pregnancy and Exposure to Study Drug Through Breastfeeding

Any pregnancy in which the estimated date of conception is either before the last visit or within 28 days of last study treatment, or any exposure to study drug through breastfeeding during study treatment or within 28 days of last study treatment, must be reported

If an adverse outcome of a pregnancy is suspected to be related to study drug exposure, this should be reported regardless of the length of time that has passed since the exposure to study treatment.

A congenital anomaly, death during perinatal period, an induced abortion, or a spontaneous abortion are considered to be an SAE and should be reported in the same time frame and in the same format as all other SAEs (see Reporting of SAEs [[Section 9.5.4.1](#)]).

Pregnancies or exposure to study drug through breastfeeding must be reported by fax or email as soon as possible but no later than 1 business day from the date the investigator becomes aware of the pregnancy. The contact information for the reporting of pregnancies and exposure to study drug through breastfeeding is provided in the Investigator Study File. The Pregnancy Report Form must be used for reporting. All pregnancies must be followed to outcome. The outcome of the pregnancy must be reported as soon as possible but no later than 1 business day from the date the investigator becomes aware of the outcome.

A subject who becomes pregnant must be withdrawn from the study.

9.5.4.3 Reporting of Events Associated With Special Situations

9.5.4.3.1 REPORTING OF ADVERSE EVENTS ASSOCIATED WITH STUDY DRUG OVERDOSE, MISUSE, ABUSE, OR MEDICATION ERROR

AEs associated with study drug overdose, misuse, abuse, and medication error refer to AEs associated with uses of the study drug outside of that specified by the protocol. Overdose, misuse, abuse, and medication error are defined as follows:

Overdose	Accidental or intentional use of the study drug in an amount higher than the protocol-defined dose
----------	--

Misuse	Intentional and inappropriate use of study drug not in accordance with the protocol
Abuse	Sporadic or persistent intentional excessive use of study drug accompanied by harmful physical or psychological effects
Medication error	Any unintentional event that causes or leads to inappropriate study drug use or subject harm while the study drug is in the control of site personnel or the subject

All AEs associated with overdose, misuse, abuse, or medication error should be captured on the AE CRF and also reported using the procedures detailed in Reporting of Serious Adverse Events ([Section 9.5.4.1](#)) even if the AEs do not meet serious criteria. Abuse is always to be captured as an AE. If the AE associated with an overdose, misuse, abuse, or medication error does not meet serious criteria, it must still be reported using the SAE form and in an expedited manner but should be noted as nonserious on the SAE form and the AE CRF.

9.5.4.3.2 REPORTING OF STUDY-SPECIFIC EVENTS

Not applicable.

9.5.4.4 Expedited Reporting

The sponsor must inform investigators and regulatory authorities of reportable events, in compliance with applicable regulatory requirements, on an expedited basis (ie, within specific time frames). For this reason, it is imperative that sites provide complete SAE information in the manner described above.

9.5.4.5 Breaking the Blind

Not applicable.

9.5.4.6 Regulatory Reporting of Adverse Events

AEs will be reported by the sponsor or a 3rd party acting on behalf of the sponsor to regulatory authorities in compliance with local and regional law and established guidance. The format of these reports will be dictated by the local and regional requirements.

All studies that are conducted within any European country will comply with European GCP Directive 2005/28/EC and Clinical Trial Directive 2001/20/EC. All SUSARs will be reported, as required, to the competent authorities of all involved European member states.

9.5.5 Completion/Discontinuation of Subjects

A subject may elect to discontinue the study at any time for any reason. All subjects who discontinue the study are to complete the study's early discontinuation procedures indicated in the Schedule of Procedures/Assessments ([Table 4](#) and [Table 5](#)).

The investigator will promptly explain to the subject involved that the study will be discontinued for that subject and provide appropriate medical treatment and other necessary measures for the subject. A subject who has ceased to return for visits will be followed up by mail, phone, or other means to gather information such as the reason for failure to return, the status of treatment compliance, the presence or absence of AEs, and clinical courses of signs and symptoms.

Subjects who discontinue early from the study will be discontinued for one of these primary reasons: AE(s), lost to follow-up, subject choice, withdrawal of consent, pregnancy, study terminated by sponsor, or other. In addition to the primary reason, the subject may indicate 1 or more secondary reason(s) for discontinuation. Study disposition information will be collected on the Subject Disposition CRF.

A subject removed from the study for any reason may not be replaced.

9.5.6 Abuse or Diversion of Study Drug

During the study, the investigator will report any concern about abuse or diversion of study drugs by completing the Abuse or Diversion of Study Drug CRF.

AEs associated with abuse or diversion will be appropriately reported as AEs and monitored per [Section 9.5.1.5.1](#). Abuse is always to be captured as an AE.

9.5.7 Confirmation of Medical Care by Another Physician

The investigator will instruct subjects to inform site personnel when they are planning to receive medical care by another physician. At each visit, the investigator will ask the subject whether he/she has received medical care by another physician since the last visit or is planning to do so in the future. When the subject is going to receive medical care by another physician, the investigator, with the consent of the subject, will inform the other physician that the subject is participating in the clinical study.

9.6 Data Quality Assurance

This study will be organized, performed, and reported in compliance with the protocol, SOPs, working practice documents, and applicable regulations and guidelines. Site audits may be conducted periodically by the sponsor's or the CRO's qualified compliance auditing team, which is an independent function from the study team responsible for conduct of the study.

9.6.1 Data Collection

Data required by the protocol will be collected on the CRFs and entered into a validated data management system that is compliant with all regulatory requirements. As defined by ICH guidelines, the CRF is a printed, optical, or electronic document designed to record all of the protocol-required information to be reported to the sponsor on each study subject.

Data collection on the CRF must follow the instructions described in the CRF Completion Guidelines. The investigator has ultimate responsibility for the collection and reporting of all clinical data entered on the CRF. The investigator or designee as identified on Form FDA 1572 must sign the completed CRF to attest to its accuracy, authenticity, and completeness.

Completed, original CRFs are the sole property of Eisai and should not be made available in any form to 3rd parties without written permission from Eisai, except for authorized representatives of Eisai or appropriate regulatory authorities.

9.6.2 Clinical Data Management

All software applications used in the collection of data will be properly validated following standard computer system validation that is compliant with all regulatory requirements. All data, both CRF and external data (eg, laboratory data), will be entered into a clinical system.

9.7 Statistical Methods

All statistical analyses will be performed by the sponsor or designee after the study is completed and the database is locked and released and a snapshot of the database is obtained and released. Statistical analyses will be performed using Statistical Analysis System (SAS) software or other validated statistical software as required. Details of the statistical analyses will be included in a separate statistical analysis plan (SAP).

9.7.1 Statistical and Analytical Plans

The statistical analyses of Core Study data are described in this section. Further details of the analytical plan will be provided in the SAP, which will be finalized before database lock.

9.7.1.1 Study Endpoints

9.7.1.1.1 PRIMARY ENDPOINT

Safety and tolerability, which include incidence of treatment-emergent adverse events (TEAEs) and SAEs, laboratory parameters, vital signs, and ECG parameters, of perampanel oral suspension in children (ages 4 to <7 years and ≥ 7 years to <12 years) with POS or PGTC

9.7.1.1.2 SECONDARY ENDPOINTS

The following endpoints will be analyzed:

1. The relationship between plasma levels of perampanel and efficacy endpoints (ie, change in average seizure frequency over 28 days, responder probability, and the proportion of subjects who are seizure-free in the Maintenance Period of the Core Study) separately for each seizure type
2. The relationship between plasma levels of perampanel and cognition endpoints including change from baseline in ABNAS, CBCL, and LGPT. In addition, depending

on the AE data, the relationship between plasma levels of perampanel and select AEs will be assessed.

3. Change from baseline at Week 23 and Week 52 in ABNAS, CBCL, and LGPT
4. Changes from baseline at Week 23 and Week 52 in growth and development parameters (height, weight, thyroid, and IGF-1)
5. Change from baseline in EEG and the frequency of EEG abnormalities during awake and sleep state
6. Proportion of subjects (aged 6 or older at time of consent/assent) with any treatment-emergent reports of suicidal ideation and behavior on the C-SSRS and intensity of these behaviors assessed using C-SSRS scores
7. The median percent change in seizure frequency per 28 days during Treatment Phase (Titration Period and Maintenance Period) of the Core Study, and during the long-term treatment (up to 52 weeks) relative to the Pretreatment Phase. Seizure frequency will be based on the number of seizures per 28 days, calculated as the number of seizures over the entire time interval divided by the number of days in the interval and multiplied by 28.
8. Proportion of responders (25% responders defined as a decrease in 28-day seizure frequency of equal or greater than 25% compared to baseline seizure frequency; 50% responders defined as a decrease in 28-day seizure frequency of equal or greater than 50% compared to baseline seizure frequency; 75% responders defined as a decrease in 28-day seizure frequency of equal or greater than 75% compared to baseline seizure frequency) during Maintenance Period of Core Study, and during the long term treatment (up to 52 weeks)
9. Proportion of subjects who are seizure-free during Maintenance Period of Core Study, and during the long-term treatment (up to 52 weeks)
10. CGI of Change

9.7.1.1.3 EXPLORATORY ENDPOINT

Change from baseline at Week 23 and Week 52 in EQ-5D-Y.

9.7.1.2 Definitions of Analysis Sets

The Safety Analysis Set is the group of subjects who received at least 1 dose of study drug and had at least 1 postdose safety assessment.

The Full Analysis Set (FAS) is the group of subjects who received at least 1 dose of study drug and had at least 1 postdose primary efficacy measurement.

PK Analysis Set is the group of subjects receiving perampanel and with at least 1 quantifiable perampanel concentration at one of the visits during the Maintenance Period of the Core Study and with adequately documented dosing history.

PK/PD Analysis Set is the group of subjects receiving perampanel who have seizure frequency, cognition, or AE data with documented dosing history. Subjects receiving perampanel should have at least 1 quantifiable perampanel concentration at one of the visits during the Maintenance Period of the Core Study as per the PK Analysis Set.

9.7.1.3 Subject Disposition

Reasons for discontinuation will be recorded for all entered subjects. The frequencies of occurrence of each reason for discontinuation will be summarized. The data will be described using incidence rate (number of subjects and percentage).

9.7.1.4 Demographic and Other Baseline Characteristics

Demographic and other baseline characteristics for the safety analysis set will be summarized using descriptive statistics. Continuous demographic and baseline variables include age, weight, height, and body mass index (BMI); categorical variables include sex, age group, race, and ethnicity.

9.7.1.5 Prior and Concomitant Therapy

All investigator terms for medications recorded in the CRF will be coded to an 11-digit code using the World Health Organization Drug Dictionary (WHO DD). The number (percentage) of subjects who took prior and concomitant medications will be summarized on the Safety Analysis Set by Anatomical Therapeutic Chemical (ATC) class and WHO DD preferred term (PT). Prior medications will be defined as medications that stopped before the 1st dose of study drug. Concomitant medications will be defined as medications that (1) started before the 1st dose of study drug and were continuing at the time of the 1st dose of study drug, or (2) started on or after the date of the 1st dose of study drug 4 weeks after the subject's last dose. All medications will be presented in subject data listings.

9.7.1.6 Efficacy Analyses

The percent change in seizure frequency per 28 days will be summarized using descriptive statistics (n, mean, median, minimum and maximum) by age cohorts (4 to <7 years, ≥ 7 to <12 years), by disease cohorts (POS, PGTC, and GTC), and by the presence or absence of concomitant EIAED in the FAS.

The proportion of subjects who are seizure-free and the proportion of responders based on decrease from baseline in 28-day seizure frequency of equal or greater than 25%, equal or greater than 50%, and equal or greater than 75% will be summarized using frequency count (number and percentage) by age cohorts (4 to <7 years, ≥ 7 to <12 years), by disease cohorts (POS, PGTC, and GTC), and by the presence or absence of concomitant EIAED in the FAS.

The CGIC will be summarized using frequency count (number and percentage) by age cohorts (4 to <7 years, ≥ 7 to <12 years), by disease cohorts (POS, PGTC, and GTC), and by the presence or absence of concomitant EIAED in the FAS.

For purposes of registration in Japan, perampanel will be determined to be efficacious if, in subjects enrolled in Japan, the upper limit of the 95% CI for the median percent change in POS frequency per 28 days is below the pre-specified threshold. This prespecified threshold consists of the median percent reduction in seizure frequency (ie, 10.5%) in subjects who received placebo during the Randomization Phase of Study E2007-J000-335. For example, if the 95% CI limits for the median percent reduction in seizure frequency are 65.0% and 25.0%, respectively, success would be declared because the upper bound of the CI falls below the prespecified threshold.

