Pharmacokinetic/Pharmacodynamic Analysis Set: The group of subjects receiving perampanel who have seizure frequency, cognition, or AE data with documented dosing history. Subjects receiving perampanel should have at least 1 quantifiable perampanel concentration at one of the visits during the Maintenance Period of the Core Study as per the PK Analysis Set.

Extension A

Safety Analysis Set: The group of subjects who received at least 1 dose of study drug and had at least 1 postdose safety assessment in the Extension A. (revised per Amendment 03)

Full Analysis Set: The group of subjects who received at least 1 dose of study drug and had at least 1 postdose seizure measurement in the Extension A. (revised per Amendment 03)

Extension B

Safety Analysis Set: The group of subjects who received at least 1 dose of study drug and had at least 1 postdose safety assessment in Extension B. (revised per Amendments 03 and 04)

Efficacy Analyses

Core Study

The percent change in seizure frequency per 28 days will be summarized using descriptive statistics (n, mean, median, minimum and maximum) by age cohorts (4 to <7 years, ≥7 to <12 years), by disease cohorts (POS, PGTC, and GTC), and by the presence or absence of concomitant EIAED in the Full Analysis Set (FAS).

The proportion of responders and the proportion of subjects who are seizure-free will be summarized using frequency count (number and percentage) by age cohorts (4 to <7 years, ≥7 to <12 years), by disease cohorts (POS, PGTC, and GTC), and by the presence or absence of concomitant EIAED in the FAS.

The CGIC will be summarized using frequency count (number and percentage) by age cohorts (4 to <7 years, ≥7 to <12 years), by disease cohorts (POS, PGTC, and GTC), and by the presence or absence of concomitant EIAED in the FAS.

For purposes of registration in Japan, perampanel will be determined to be efficacious if, in subjects enrolled in Japan, the upper limit of the 95% CI for the median percent change in POS frequency per 28 days is below the pre-specified threshold. This pre-specified threshold consists of the median percent reduction in seizure frequency (ie, 10.5%) in subjects who received placebo during the Randomization Phase of Study E2007-J000-335.

Extension A

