Safety analyses will be performed similarly to the Core Study analyses and all analyses will be on the perampanel treatment duration (Core Study and Extension A). (revised per Amendment 03) The incidence of TEAEs, SAEs, AEs associated with fatal outcomes or leading to discontinuations, and AEs leading to dose adjustment will be summarized. Laboratory parameters, vital signs, and ECG parameters will be summarized. Change from baseline in CBCL, ABNAS, and LGPT, change from baseline in growth parameters, change from baseline in EEG parameters, the frequency of EEG abnormalities, and the proportion of subjects with any treatment-emergent report of suicidal ideation and behavior and intensity of these behaviors, will also be summarized descriptively. Baseline for these parameters is the last non-missing value before the 1st perampanel dose.

Extension B

Safety analyses for Extension B are described in [Appendix 2](#). (revised per Amendments 03 and 04)

Exploratory Analyses

The change from baseline in EQ-5D-Y at Week 23 and Week 52 will be summarized.

Interim Analyses

An independent data monitoring committee (DMC) will be constructed to monitor the safety data. The responsibilities, membership, and purpose of the DMC, the timing of the meeting(s), and an outline of the plan for review of the safety data will be documented in the DMC Charter.

Analyses for regional submissions may be performed during the course of the study. (revised per Amendment 02)

Sample Size Rationale

A sample size of at least 160 subjects (with up to 40 subjects with PGTC and the balance with POS), is deemed sufficient for safety evaluation in this age group (age 4 to <12 years). (revised per Amendment 02) This sample size matches the total number of adolescents who were enrolled in the 4 global Phase 3 efficacy and safety studies that support the POS and PGTC indications.

For purposes of registration in Japan, it has been determined that a sample size of 65 subjects enrolled in Japan will provide 80% power to exclude the possibility that there would be a reduction smaller than that observed in the placebo arm of Study E2007-J000-335 (ie, 10.5%).

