9.7.2 Determination of Sample Size

A sample size of at least 160 subjects (with up to 40 subjects with PGTC and the balance with POS), is deemed sufficient for safety evaluation in this age group (age 4 to <12 years). (revised per Amendment 02) This sample size matches the total number of adolescents who were enrolled in the 4 global Phase 3 efficacy and safety studies that support the POS and PGTC indications.

For purposes of registration in Japan, it has been determined that a sample size of 65 subjects enrolled in Japan will provide 80% power to exclude the possibility that there would be a reduction smaller than that observed in the placebo arm of Study E2007-J000-335 (ie, 10.5%). Details are provided in the SAP.

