## 4 DETERMINATION OF SAMPLE SIZE

A sample size of 160 subjects (with up to 40 subjects with PGTC and the balance with POS), is deemed sufficient for safety evaluation in this age group (age 4 to <12 years). This sample size matches the total number of adolescents who were enrolled in the 4 global Phase 3 efficacy and safety studies that support the POS and PGTC indications.

For purposes of registration in Japan, it has been determined that a sample size of 65 subjects enrolled in Japan will provide 80% power to exclude the possibility that there would be a reduction smaller than that observed in the placebo arm of Study E2007-J000-335 (ie, 10.5%).

The sample size calculation was examined based on two scenarios of 10%, 40% and 50% or 10%, 30% and 60% of subjects receiving E2007 doses of 4mg, 8mg or 12mg respectively, as allocation group dose. In addition, the ratio of inducer medication user was assumed to be 70%. In either scenario, a sample size set 65 subjects is powered above 80%. The power is calculated from the number of counts from 10,000 re-sampling simulation about the upper limit of 95% confidence interval below 10.5%.

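### The Japan registration rule is wrong as printed: an upper limit for percent change is set against an unsigned 10.5% reduction, and the worked example fails for either limit shown

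*Protocol*

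**What the plan says.** Protocol 9.7.1.6 sets the criterion for subjects enrolled in Japan: success if "the upper limit of the 95% CI for the median percent change in POS frequency per 28 days is below the pre-specified threshold". It then defines the cut-off: "This prespecified threshold consists of the median percent reduction in seizure frequency (ie, 10.5%) in subjects who received placebo" in Study E2007-J000-335. The Synopsis (Efficacy Analyses) has the same rule and the same definition.

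Only 9.7.1.6 adds an example: "if the 95% CI limits for the median percent reduction in seizure frequency are 65.0% and 25.0%, respectively, success would be declared" and gives as the reason "because the upper bound of the CI falls below the prespecified threshold".

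The aim is stated in words in the Synopsis (Sample Size Rationale), in Protocol 9.7.2 and in Core SAP section 4: 65 subjects in Japan give 80% power to "exclude the possibility that there would be a reduction smaller than that observed in the placebo arm", that is, 10.5%. Core SAP section 4 then describes how power was counted, from a "re-sampling simulation about the upper limit of 95% confidence interval below 10.5"%, with no sign and no scale in that sentence.

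Core SAP 5.4.2 asks for a median and 95% CI of percent change in Japan, but gives no threshold and no success rule. Extension SAP 5.4.2 repeats the analyses for Japan and gives none either.

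**The concern.** Percent change and percent reduction have opposite signs. A rule that an upper limit must lie below a value suits change, where benefit is negative. A positive 10.5% suits reduction, where benefit is positive and the lower limit is the one that must clear the threshold. The printed rule takes one half from each scale, and the example, which should settle the matter, gives a reason that is untrue.

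The other efficacy analyses are descriptive. This rule serves secondary objective 6 and is the only efficacy criterion with a yes/no answer. The programming specifications and table shells are separate documents and were not available, so there is no evidence that the rule was miscoded. The point is that the governing text does not state the test correctly anywhere, and the same unsigned figure underlies the power statement.

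**Working it through.** **1. Where 10.5% appears.** It is printed six times in the current text, never with a minus sign.

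| Place | Use | Correct unsigned? |
|---|---|---|
| Synopsis, Sample Size Rationale | reduction to be exceeded | yes |
| Protocol 9.7.2 | reduction to be exceeded | yes |
| Core SAP 4, first use | reduction to be exceeded | yes |
| Synopsis, Efficacy Analyses | value an upper limit must lie below | no |
| Protocol 9.7.1.6 | value an upper limit must lie below | no |
| Core SAP 4, last sentence | value an upper limit must lie below | no |

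**2. The example.** As printed, 65.0 < 10.5 is false and 25.0 < 10.5 is false. With signs restored the interval for change is −65.0% to −25.0%, and −25.0 < −10.5 is true, with a margin of 25.0 − 10.5 = 14.5 points. Since −25.0 is also below +10.5, the example would not separate the intended rule from the literal one even with its signs restored.

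**3. Three readings of the rule.**

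- Intended: upper limit of change < −10.5%, equivalent to lower limit of reduction > 10.5%. This matches the stated aim.
- Literal, change scale: upper limit of change < +10.5%. An interval of −30% to 0% passes although it does not exclude a reduction smaller than 10.5%. The decision differs from the intended one whenever the upper limit falls between −10.5% and +10.5%.
- Literal, reduction scale: upper limit of reduction < 10.5%. This declares success only when the drug is shown to be worse than the placebo figure. The plan's own example would fail, because 65.0 is not below 10.5.

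**4. The plan's own figure.** The 80% power cannot be reproduced. Core SAP section 4 gives dose mixes (10/40/50% or 10/30/60% at 4/8/12 mg) and a 70% inducer share, but no effect size, spread or CI formula. It therefore cannot be seen from the text which sign the simulation used.

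**5. Illustration of a literal coding (hypothetical).** Assume an order-statistic 95% CI for the median. With n = 65 the limits are the 25th and 41st ordered values (coverage 0.9536). The upper limit is below t when at least 41 of 65 subjects lie below t, so P(success) = P(Bin(65, p) ≥ 41) with p = P(change < t). Take a drug equal to the Study 335 placebo, with true median change −10.5%.

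- Intended rule, t = −10.5%: p = 0.5 and P = 0.0232, whatever the spread.
- Literal change scale, t = +10.5%, log-normal frequency ratio with log-SD σ (assumed): p = Φ(ln(1.105/0.895)/σ) = Φ(0.211/σ).

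| σ | 0.3 | 0.5 | 0.8 | 1.0 | 1.5 |
|---|---|---|---|---|---|
| P(success) | 0.993 | 0.756 | 0.379 | 0.260 | 0.138 |

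A 40,000-replicate simulation gave 0.993, 0.756, 0.380, 0.261 and 0.135. With normally distributed change and assumed SDs of 30, 40, 50 and 60 points, the exact values are 0.993, 0.911, 0.753 and 0.595.

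A signed-rank (Hodges-Lehmann) interval, one possible meaning of the rank transformation mentioned in Core SAP 5.3.5.1, gives 0.998 to 0.005 over the same log-SDs, against at most 0.007 under the intended rule. It estimates the pseudomedian, which lies above the median under this skew.

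On the literal reduction scale, a drug with a true 30% reduction would succeed with probability of about 0 (normal data, SD 30 to 60).

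**The case against.** The best defence is that the text never prints +10.5% as a change. It names a reduction, and a 10.5% reduction is a change of −10.5%. On that reading the rule is coherent and correct. The order of the example's limits, 65.0% then 25.0%, suggests lower and upper limits of change with the minus signs left off, and its declared outcome is right. No passage supports the opposite direction. The revision history records that version 4.0 made the threshold positive to correct an error, so the missing sign was deliberate. The analysis is secondary, and the illustration's range is too wide to say anything about this trial.

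Much of this stands. The intent is recoverable, a coding error has not been shown, and the probabilities are hypothetical. The unnamed CI method is a side issue.

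What does not stand is that the text is therefore adequate. The charitable reading supplies signs that neither the rule nor the example prints, and the example's stated reason remains untrue. Taking the scale of Core SAP section 4 from its preceding paragraph makes matters worse: on the reduction scale, an upper limit below 10.5 points the wrong way. The version 4.0 entry explains how the positive number arose. It does not reconcile that number with an upper-limit rule for change.

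**Conclusion.** The concern holds and must be fixed. The decision threshold for the only pass/fail efficacy criterion is wrong as printed in the Synopsis and in Protocol 9.7.1.6. The example is false for either printed limit, and neither SAP states a signed rule. These conclusions rest on the text alone and need no assumption.

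If +10.5% were applied literally to change, a placebo-equivalent drug would succeed 14% to 99% of the time, against 2.3% under the intended rule. Those figures assume the order-statistic interval and log-SDs of 1.5 down to 0.3. They show what the sign is worth and do not predict what was done.

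**What to change.** - **Synopsis and Protocol 9.7.1.6:** declare success when the upper bound of the two-sided 95% interval on median percent change in POS frequency lies under −10.5%; on the reduction scale the same test is a lower bound above 10.5%. Change the sign and the scale word together, so that a negative reduction is not reintroduced.
- **Example in 9.7.1.6:** give percent-change limits of −65.0% and −25.0%.
- **Core SAP 5.4.2:** add the same rule in one sentence and name the CI method there.
- **Core SAP section 4:** put the sign and the scale on the simulation criterion.
- **Simulation:** check that the 10,000-resample program used −10.5% on the change scale. Restate the power only if it did not.

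The cost is one corrected threshold in two Protocol places, one example, two SAP sentences and a check of an existing program, made through the written amendment or administrative change that Protocol 11.1 requires. A re-run is needed only if the simulation used the other sign.
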